2.8.4 Other safety data

2.8.4.1 ECG and cardiac imaging data

Data handling

In case the study requires ECG replicates at any assessment, the average of the ECG parameters at that assessment should be used in the analyses.

Data analysis

12-lead ECGs including PR, QRS, QT, QTcF and RR intervals will be obtained central/local for each subject during the study. ECG data will be read and interpreted locally.

The number and percentage of subjects with notable ECG values will be presented.

- QT, QTcF
 - New value of > 450 and \leq 480 ms
 - New value of > 480 and \leq 500 ms
 - New value of > 500 ms
 - Increase from Baseline of > 30 ms to \leq 60ms
 - Increase from Baseline of > 60 ms
- HR
 - Increase from baseline >25% and to a value > 100 bpm
 - Decrease from baseline >25% and to a value < 50 bpm
- PR
 - Increase from baseline >25% and to a value > 200 ms
 - New value of > 200 ms
- QRS
 - Increase from baseline >25% and to a value > 120 ms
 - New values of QRS > 120 ms

2.8.4.2 Vital signs

Vital sign assessments are performed in order to characterize basic body function. The following parameters were collected: height (cm), weight (kg), body temperature ($^{\circ}$ C), heart rate (beats per minute), systolic and diastolic blood pressure (mmHg)

Data handling

Vital signs collected on treatment will be summarized.

Data analysis

For analysis of vital signs the clinically notable vital sign criteria are provided in [Table 2-6](#) below.

Table 2-5 Clinically notable changes in vital signs

Vital sign (unit)	Clinically notable criteria	
	above normal value	below normal value
Weight (kg)	increase > 10% from Baseline	decrease > 10% from Baseline
Systolic blood pressure (mmHg)	>=180 with increase from baseline of >=20	<=90 with decrease from baseline of >=20
Diastolic blood pressure (mmHg)	>=105 with increase from baseline of >=15	<=50 with decrease from baseline of >=15
Pulse rate (bpm)	>=100 with increase from baseline of >25%	<=50 with decrease from baseline of > 25%
Body temperature	>= 39.1	-

The number and percentage of subjects with notable vital sign values (high/low) will be presented.

2.9 Pharmacokinetic endpoints

PK Concentrations

Descriptive statistics (n, m (number of non-zero concentrations), mean, CV% mean, SD, median, geometric mean, CV% geo-mean, minimum and maximum) for PDR001 concentrations will be presented at each scheduled time point for the Pharmacokinetic analysis set. For PDR001, pre-dose concentrations collected before dose administration on Day 1 of Cycle 2+ are C_{trough}.

All individual PDR001 concentration data will be listed for the Safety set.

Handling of PK data below LLOQ or missing

All concentration values below the lower limit of quantitation (LLOQ) (i.e. <0.25 ng/mL) are set to zero by the Bioanalyst, and will be displayed in the listings as zero and flagged. LLOQ values will be treated as zero in any calculations of summary statistics, and treated as missing for the calculation of the geometric means and their CV%.

Missing values for any PK data will not be imputed and will be treated as missing.

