2.3 Rationale for dose and regimen selection

In study [CPDR001X2101], PDR001 single-agent was administered as an intravenous infusion over 30 minutes at doses ranging from 1 to 10 mg/kg on an every 2 weeks (Q2W) schedule or at 3 and 5 mg/kg every 4 weeks (Q4W) schedules. Approximately dose-proportional increase in exposure (C1D1 AUC0-336) was observed with doses from 1 to 10 mg/kg and no DLTs were observed. Accumulation of approximately 2.1-3.4-fold was observed with Q2W dosing and 1.6-2.2-fold with Q4W dosing. Population PK analysis indicated that the changes in exposure due to patient weight differences are minimal across the anticipated weight range of 30 to 150 kg for the patient population. Therefore, a flat dosing scheme was selected. Two recommended phase II dosing regimens have been established: 300 mg Q3W and 400 mg Q4W flat dosing schedules. A flat dose of 400 mg Q4W or 300 mg Q3W is expected to achieve a mean steady-state C_{trough} value higher than the ex vivo EC₅₀ for antigen-stimulated IL-2 production, a translational biomarker for PD-1 blockade (Patnaik et al, 2015). Based on the safety profile observed in study [CPDR001X2101] (Section 1.2) and the expected C_{trough} values, 400 mg Q4W is expected to be a safe and efficacious dose.

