6.1.1 Dosing regimen

Table 6-1 Dose and treatment schedule

Study treatments	Pharmaceutical form and route of administration	Strength	Frequency and/or Regimen	Dose Administered
PDR001	Powder for solution for infusion in vial for i.v. infusion	4 x 100 mg vials	Every 4 weeks	400 mg

PDR001 will be administered via intravenous infusion over 30 minutes (up to 2 hours, if clinically indicated) once every 4 weeks (+/- 7 days window). PDR001 will be administered on Day 1 of every cycle. Each cycle is 28 days. The actual date of Cycle Day 1 will be used to project the dates of future cycles. The dose may be interrupted for up to 12 weeks. The safety assessments (as per [Table 7-1](#) and [Section 7.2.2](#)) should be performed according to the actual day of infusion.

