10.5.4 Pharmacokinetics

Descriptive statistics (n, m (number of non-zero concentrations), mean, CV%, SD, median, geometric mean, geometric CV%, minimum and maximum) for PDR001 concentrations will be presented at each scheduled timepoint. For PDR001, pre-dose concentrations collected before dose administration on Day 1 of Cycle 2+ are Ctrough.

All concentration data for PDR001 will be displayed graphically.

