2.2 Analysis sets

Full Analysis Set

The Full Analysis Set (FAS) comprises all patients to whom study treatment has been assigned and who received one dose of any study treatment (i.e. at least one dose of PDR001 (including incomplete infusion)).

Patients will be analyzed according to the treatment they have been assigned to.

Safety

The Safety Set is defined in the same way as the FAS and includes all patients who received at least one dose of study treatment (i.e. at least one dose of the PDR001 (including incomplete infusion)).

Pharmacokinetic analysis set (PAS)

The Pharmacokinetic analysis set (PAS) includes all patients who provide at least one evaluable PDR001 PK concentration. For a concentration to be evaluable, patients are required to:

- receive one of the planned treatments of PDR001 prior to sampling
- for pre-dose samples, have the sample collected before the next dose administration
- for end-of-infusion samples, have the sample collected within 2 hours post end of infusion

Immunogenicity (IG) analysis sets

The Immunogenicity prevalence set includes all subjects in the Full analysis set with a determinant baseline IG sample or at least one determinant post-baseline IG sample.

The Immunogenicity incidence set includes all subjects in the Immunogenicity prevalence set with a determinant baseline IG sample and at least one determinant post-baseline IG sample.

See Section 2.9.1.1 for the definition of determinant.

Patient Classification:

Patients may be excluded from the analysis populations defined above based on the protocol deviations entered in the database and/or on specific subject classification rules defined in [Table 2-3](#).

Table 2-2 Subject classification based on protocol deviations and non-PD criteria

Analysis set	Protocol deviations leading to exclusion	Non protocol deviation leading to exclusion
FAS	No written inform consent	No dose of study medication
Safety set	No written inform consent	No dose of study medication
PK Analysis Set	No written inform consent	No evaluable concentration
Immunogenicity prevalence set	No written inform consent	No determinant baseline or post-baseline IG samlpe

Immunogenicity incidence set	No written inform consent	No determinant baseline and post-baseline IG sample
------------------------------	---------------------------	---

Withdrawal of Informed Consent

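### Ctrough has no limit on time since the previous dose, so samples drawn after a dose interruption enter the Q4W trough summary and can lower it

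*SAP*

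**What the plan says.** The label depends on the cycle and day, not on elapsed time. Protocol 10.5.4 states that "pre-dose concentrations collected before dose administration on Day 1 of Cycle 2+ are Ctrough", and SAP 2.9 likewise takes "pre-dose concentrations collected before dose administration on Day 1 of Cycle 2" and later cycles as Ctrough, with summaries at each scheduled time point.

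The rules for an evaluable concentration (SAP 2.2; identical in Protocol 10.1.5) ask the patient to "receive one of the planned treatments of PDR001 prior to sampling" and, "for pre-dose samples, have the sample collected before the next dose administration". Any earlier planned dose satisfies the first condition. The second only places the sample before the next dose. For end-of-infusion samples the same list does set a limit, of 2 hours.

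On dosing, Protocol 6.1.1 specifies infusion "once every 4 weeks (+/- 7 days window"), and adds "The dose may be interrupted for up to 12 weeks" and "The actual date of Cycle Day 1 will be used to project the dates of future cycles". The footnotes to Protocol Table 7-7 require pre-dose samples on the day of infusion, immediately before it starts.

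The PK objective (Protocol Table 3-1, SAP Table 1-1) is to characterize PDR001 at 400 mg Q4W, with Ctrough given as the example parameter.

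**The concern.** Because cycles are re-projected from actual dosing dates, the first infusion after an interruption is still Day 1 of the next cycle. Its pre-dose sample is drawn after the whole delay, passes the evaluability rules and is tabulated as that cycle's Ctrough. Such delays are foreseeable: many toxicity rules in Protocol 6.3.1 interrupt PDR001 and allow up to 12 weeks for recovery.

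Concentration keeps falling after the nominal 4-week trough, so error from interruptions runs in one direction and does not average out. A table that mixes 4-week values with 8- to 16-week values does not describe exposure under Q4W dosing, which is the stated objective. The dose rationale in Protocol 2.3 also rests on an expected mean steady-state Ctrough above an ex vivo EC50, so readers are likely to set the reported mean against that argument.

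**Working it through.** The plan gives no target value, precision or sample size for Ctrough, so there is no figure to reproduce. The check is of direction and size.

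**Inputs from the documents.** Nominal interval 28 days, window ± 7 days, interruption up to 12 weeks (Protocol 6.1.1). Accumulation "1.6-2.2-fold with Q4W dosing" and 2.1-3.4-fold with Q2W dosing (Protocol 2.3).

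**Assumptions.** One-compartment (mono-exponential) decline. The share f of delayed samples at a time point is assumed, because the documents give none.

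**Step 1: half-life.** With R = 1/(1 − exp(−28k)), exp(−28k) = 1 − 1/R.
- R = 1.6: exp(−28k) = 0.375, half-life 19.8 days.
- R = 2.2: exp(−28k) = 0.545, half-life 32.0 days.

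The same calculation on the Q2W range (interval 14 days) gives 15.0 to 27.9 days, which overlaps.

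**Step 2: one sample relative to the day-28 trough.** Ratio r = exp(−k(d − 28)), with d the days since the last dose.

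| Days since last dose | Half-life 19.8 d | Half-life 32.0 d |
|---|---|---|
| 21 (7 days early) | 1.28 | 1.16 |
| 35 (7 days late) | 0.78 | 0.86 |
| 56 | 0.38 | 0.55 |
| 84 (12 weeks) | 0.375² = 0.14 | 0.545² = 0.30 |
| 112 (16 weeks) | 0.375³ = 0.05 | 0.545³ = 0.16 |

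The Q2W-derived half-lives would give 0.07 to 0.25 at day 84.

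**Step 3: effect on the summary.** If a share f of samples has ratio r and the rest sit at the day-28 value, the arithmetic mean shifts by f(r − 1) and the geometric mean by r^f − 1. For samples at day 84:

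| Assumed share f | Arithmetic mean | Geometric mean |
|---|---|---|
| 5% | −3.5% to −4.3% | −5.9% to −9.3% |
| 10% | −7.0% to −8.6% | −11.4% to −17.8% |

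For example, at f = 10% and r = 0.141: 0.10 × (0.141 − 1) = −8.6%, and 0.141^0.10 − 1 = −17.8%.

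**Step 4: does anything else remove these samples?** A note in SAP 2.10.1.1 mentions PK concentrations flagged for exclusion, but no criterion is stated. The population PK model in Protocol 10.5.4.2 is optional and leaves the descriptive tables unchanged. The gap stands.

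**The case against.** The strongest reply concerns size. A reader might infer that the reported Q4W trough will be materially biased downward, or take 5-16% as a measure of that bias. The documents support neither. The ratios describe single samples, and the effect on a mean depends on how many samples follow an interruption, which is not given. The 5-16% figure needs 112 days since the last dose. Under Protocol 6.3.1.1 the 12-week clock starts when an immune-related event reaches the grade requiring interruption, so on that route resumption falls no later than about 12 to 16 weeks after the last dose, depending on when in the cycle the event began. Sixteen weeks is the far boundary. Patients who do not recover in time stop permanently and give no further Day 1 sample.

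Other points also stand. Samples up to 7 days early are within the window and push the trough up, so only the interruption tail is one-sided. The half-life is inferred. The SAP reports the median, minimum and maximum and lists every concentration, so a careful reader could see outlying values, and the median is little affected by a few of them. Summarizing troughs under the regimen as actually given would be defensible if labelled that way.

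None of this supplies a time limit. The objective is worded for Q4W dosing, the table carries no such label, and an exclusion flag without criteria leaves the decision until after the data are seen.

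**Conclusion.** The point holds as a defect in the definition. Followed as written, the rule places post-interruption concentrations in the Q4W Ctrough summary, where they can lower the mean and geometric mean and inflate the CV%. That conclusion comes from the text alone.

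The size is conditional on mono-exponential decline, a half-life derived from the accumulation range, and an assumed 5-10% of samples at day 84. On those terms the loss is modest for the arithmetic mean and larger for the geometric mean. With fewer or shorter interruptions it would be smaller. Incomplete infusions raise the same question of what counts as the previous dose, but the documents allow no estimate of their effect.

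Ctrough is an example parameter in a descriptive secondary objective, so the ORR analysis and its success criteria are untouched. The correction is worth making but not critical.

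**What to change.** In SAP 2.9, and in the PK analysis set rule in SAP 2.2, count a pre-dose sample as evaluable Ctrough only if it was drawn 28 ± 7 days after the previous complete infusion. This borrows the dosing window already in Protocol 6.1.1. Name it as an explicit criterion for the exclusion flag, and list out-of-window pre-dose values outside the Ctrough summary.

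No new data are needed: Protocol 7.2.7 has exact dose and sampling times recorded, and SAP 2.4.1 draws on the record of stopped or paused infusions. Retained samples would then lie between about 0.78 and 1.28 times the day-28 value (half-life 19.8 days) or 0.86 and 1.16 times (32.0 days), with deviations in both directions.

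The cost is about one sentence and the loss of a few samples from the table. The remedy is partial: the first cycles after an interruption may still read somewhat low, because some accumulation has been lost. The change concerns the analysis definition only and leaves the dosing and interruption rules as they are.

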2.10 PD and PK/PD analyses

2.10.1 Immunogenicity

2.10.1.1 Sample ADA Status

Each IG sample is assessed in a three tiered anti-drug anti-body (ADA) testing approach. All IG samples are analyzed in the initial screening assay (first tier). Samples testing negative in the screening assay are not subject to a confirmatory assay. Samples testing positive in the screening assay are then subjected to the confirmatory assay to demonstrate that ADA are specific for the therapeutic protein product (second tier). The titer of confirmatory positive samples will be subsequently determined in the titration assay (third tier). Samples identified as positive in the confirmatory assay are considered ADA positive and are further characterized in the neutralization assay to indicate the presence of neutralizing antibodies (NAb). Samples can test negative in either the screening or confirmatory assay but for analysis purposes they are not differentiated. The following properties of each sample will be provided in the source data:

- Result of assay according to pre-specified confirmatory cut point: ADA positive (yes) or ADA negative (no)
- Titer (for positive samples): numerical representation of the magnitude of the ADA response
- Presence of Nab (for positive samples, if NAb assay results are available): yes or no
- Drug tolerance level: highest drug concentration that does not interfere in the ADA detection method
- Fold titer change (i.e. x-fold): threshold for determining treatment boosted

Sample ADA status is determined based on the following definitions:

- *ADA-inconclusive sample*: Sample where assay is ADA negative and *PDR001* PK concentration at the time of IG sample collection is greater than or equal to the drug tolerance level or missing.
- *Unevaluable sample*: Sample where assay is not available.
- *Determinant sample*: Sample that is neither ADA-inconclusive nor unevaluable.

The following definitions apply only to determinant samples:

- *ADA-negative sample*: Determinant sample where assay is ADA negative and *PDR001* PK concentration at the time of IG sample collection is less than the drug tolerance level.
- *ADA-positive sample*: Determinant sample where assay is ADA positive.
 - *ADA-positive NAb sample*: Determinant sample where assay is ADA positive and presence of NAb = yes.

The following definitions apply only to post-baseline ADA-positive samples with a corresponding determinant baseline sample. To be classified as *treatment-boasted* or *treatment-unaaffected*, both the post-baseline and baseline titer must be non-missing:

[figure not shown]
- *treatment-induced ADA-positive sample*: ADA-positive sample post-baseline with ADA-negative sample at baseline.
- *treatment-boosted ADA-positive sample*: ADA-positive sample post-baseline with titer that is at least the fold titer change greater than the ADA-positive baseline titer.
- *treatment-unaaffected ADA-positive sample*: ADA-positive sample post-baseline with titer that is less than the fold titer change greater than the ADA-positive baseline titer.

NOTE: PK concentrations which are flagged for exclusion will still be used to determine ADA-inconclusive and ADA-negative samples.

The following summaries of ADA sample status (n and %) will be provided using *Immunogenicity prevalence set*:

- ADA-positive samples (i.e. ADA prevalence) and ADA-positive NAb samples, both overall and by time point (including baseline). For summaries by time point, the denominator is the number of subjects at that time point with a determinant sample.

Listings will be provided of sample ADA status (including titer for positive samples).

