Day of cycle	Category	Protocol Section	Screening period	Treatment period (cycle = 28 days)			Follow-up period						Survival F/U (after safety and efficacy follow-up)
			Screening	Cycle 1 Day 1	Subsequent cycles Day 1	EoT	30-Day Safety follow-up Visit	60-Day Safety follow-up phone call	90-Day Safety follow-up phone call	120-Day Safety follow-up phone call	150-Day safety follow-up visit / phone call (visit for WOCBP and phone call for all others)	End of post treatment follow-up	
			-28 to -1	1	1								Every 3 months

After the primary analysis cut-off date (10-Aug-2018): ePROs collection will no longer be performed.
													
EQ-5D-5L	D	7.2.10	X		
Before the primary analysis cut-off date (10-Aug-2018): Treatment Period: Every 8 weeks from Cycle 3 Day 1 for the first 13 cycles and every 12 weeks from Cycle 13 Day1 thereafter EOT: Collect at EOT Visit 30-day SafetyVisit: Collect at 30-Day Safety Follow-up Visit Efficacy follow-up: Continue same schedule as during treatment period until BIRC confirmed irRECIST progression After the primary analysis cut-off date (10-Aug-2018): ePROs collection will no longer be performed
								
Study Drug Administration													
Study Drug administration	D			X									
Verification for treatment beyond RECIST 1.1	D	6.1.5.1		X									

	Category	Protocol Section	Screening period	Treatment period (cycle = 28 days)			Follow-up period						
			Screening	Cycle 1 Day 1	Subsequent cycles Day 1	EoT	30-Day Safety follow-up Visit	60-Day Safety follow-up phone call	90-Day Safety follow-up phone call	120-Day Safety follow-up phone call	150-Day safety follow-up visit / phone call (visit for WOCBP and phone call for all others)	End of post treatment follow-up	Survival F/U (after safety and efficacy follow-up)
Day of cycle			-28 to -1	1	1								Every 3 months
progression (if necessary)													
Blood sampling for PK	D	7.2.7		
Before the primary analysis cut-off date (10-Aug-2018): Treatment period: At Day 1 of all cycles until Cycle 13 and Day 1 of every 6 cycles thereafter until Cycle 25 EOT 30-Day safety follow-up 150-Day safety follow-up for WOCBP Unscheduled: At the time of PD based on RECIST 1.1 At the time of PD based on irRECIST After the primary analysis cut-off date (10-Aug-2018): No additional PK samples will be collected for the patients still ongoing on the study, unless requested by the Investigator.
									

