Immunogenicity (IG) sampling	D	7.2.7		
Before the primary analysis cut-off date (10-Aug-2018): Treatment period: At Day 1 of all cycles until Cycle 13 and Day 1 of every 6 cycles thereafter until Cycle 25 EOT 30-Day safety follow-up 150-Day safety follow-up for WOCBP Unscheduled:
									

	Category	Protocol Section	Screening period	Treatment period (cycle = 28 days)			Follow-up period					
			Screening	Cycle 1 Day 1	Subsequent cycles Day 1	EoT	30-Day Safety follow-up Visit	60-Day Safety follow-up phone call	90-Day Safety follow-up phone call	120-Day Safety follow-up phone call	150-Day safety follow-up visit / phone call (visit for WOCBP and phone call for all others)	End of post treatment follow-up
Day of cycle			-28 to -1	1	1							Every 3 months
				At the time of PD based on RECIST 1.1 At the time of PD based on irRECIST At the time of suspected irAEs After the primary analysis cut-off date (10-Aug-2018): No additional IG samples will be collected for the patients still ongoing on the study, unless requested by the Investigator.								
Follow-up												
Survival follow-up		7.1.9										X
Antineoplastic therapies since discontinuation of study treatment	D	7.1.9				X	X	X	X	X		X

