7.2.7 Pharmacokinetics and immunogenicity (IG) assessment

The exact date and clock times of drug administration PK and IG blood draw will be recorded on the appropriate eCRF.

Blood samples will be taken by either direct venipuncture or an indwelling cannula inserted in a forearm vein opposite to the arm used for infusion.

A total of 5 mL of blood will be collected for PDR001 PK and IG analysis in serum (2 mL for PDR001 PK and 3 mL for IG).

For time points when PDR001 (mAb) PK and IG are to be measured, a single blood sample will be collected for both IG and PDR001 PK (Table 7-7). After clotting, the resulting serum will be separated in aliquots and will be stored frozen until analysis.

Refer to the [Laboratory Manual] for detailed instructions for the collection, handling, and shipment of PK and IG samples.

If patients experience a SAE or an AE leading to the discontinuation of the study treatment, an unscheduled PK blood sample should be obtained as close as possible to the event occurrence. If patients experience suspected immunologically related AE such as infusion-related reaction, hypersensitivity, cytokine release syndrome and anaphylaxis, an unscheduled IG blood sample should be obtained as close as possible to the event occurrence. The date and time of the last dose and the time of PK blood draw should be recorded.

After the primary analysis cut-off date (10-Aug-2018), no additional PK and IG samples will be collected for the patients still ongoing on the study, unless requested by the Investigator.

Table 7-7 Pharmacokinetic and immunogenicity blood collection log

Cycle	Day	Scheduled timepoint (hours)	Dose reference ID	PK Sample number	IG Sample number
1	1	Predose/0hrs ^a	1	101	201
1	1	End-of-Infusion ^b	1	102	
2	1	Predose/0hrs	2	103	202
3	1	Predose/0hrs	3	104	203
3	1	End-of-Infusion ^b	3	105	
4	1	Predose/0hrs	4	106	204
5	1	Predose/0hrs	5	107	205
6	1	Predose/0hrs	6	108	206
7	1	Predose/0hrs	7	109	207
8	1	Predose/0hrs	8	110	208
9	1	Predose/0hrs	9	111	209
10	1	Predose/0hrs	10	112	210
11	1	Predose/0hrs	11	113	211
12	1	Predose/0hrs	12	114	212
13	1	Predose/0hrs	13	115	213
19	1	Predose/0hrs	14	116	214
25 ^c	1	Predose/0hrs	15	117	215
EoT	N/A	Anytime	N/A	118	216
30-Day Safety F/U visit	N/A	Anytime	N/A	119	217
150-Day Safety F/U visit (for women of childbearing potential)	N/A	Anytime	N/A	120	218

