
 • Unscheduled^d • Unscheduled at the time of PD based on RECIST 1.1^e • Unscheduled at the time of PD based on irRECIST^e • Unscheduled at the time of suspected irAE (only IG sample) 	N/A	Anytime	N/A	1001+	2001+

^aAll predose samples must be collected immediately prior to starting the infusion (day of infusion)

^bEnd-of-infusion samples should be collected within 30 minutes post-infusion.

^cPK and immunogenicity samples will not be collected after cycle 25 even if the patient continues treatment beyond cycle 25.

^dUnscheduled PK and immunogenicity samples may be collected at any time if clinically indicated or at the Investigator's discretion and must be sequentially numbered as 1001, 1002, 1003, etc. for PK samples, and 2001, 2002, 2003, etc. for immunogenicity samples.

^eAn unscheduled PK sample and an unscheduled immunogenicity sample should be collected upon confirmed disease progression based on RECIST 1.1 and irRECIST.

[figure not shown]
Immunogenicity samples are collected together with PK samples. **After the primary CSR data cut-off date no additional PK and IG samples will be collected for the patients still ongoing on the study, unless requested by the**

[figure not shown]
[figure not shown]
Cycle	Day	Scheduled timepoint (hours)	Dose reference ID	PK Sample number	IG Sample number
Investigator. Blood samples are collected from the arm opposite from infusion site.					

[figure not shown]

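### An ADA-negative sample without a PK result is set aside while a positive one counts: a minor flaw for IG-only irAE draws and for baselines whose PK result is lost

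*SAP*

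**What the plan says.** **Collection.** Protocol Section 7.2.7, Table 7-7, lists the draw as "Unscheduled at the time of suspected irAE (only IG sample". Table 7-1 in Section 7.1 agrees. Its IG row includes "At the time of suspected irAEs" among the unscheduled triggers. Its PK row has no such trigger and its list ends with "At the time of PD based on irRECIST After the primary analysis cut-off date (10-Aug-2018): No additional PK samples will be collected". The text of Section 7.2.7 asks for an IG sample at events such as infusion reaction, hypersensitivity, cytokine release syndrome or anaphylaxis. Separately, it asks for a PK sample at an SAE or at an AE that ends study treatment. Against this, the note under Table 7-7 says "Immunogenicity samples are collected together with PK samples". The text adds that where both are to be measured "a single blood sample will be collected for both IG and PDR001 PK".

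**Classification.** Under SAP 2.10.1.1 a negative assay is inconclusive if the "PK concentration at the time of IG sample collection is greater than or equal to the drug tolerance level or missing". Inconclusive samples are not determinant. An ADA-positive sample is a "Determinant sample where assay is ADA positive", with no PK condition. For summaries by time point, "the denominator is the number of subjects at that time point with a determinant sample". The denominator for the overall summary is not stated.

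**Related rules.** SAP 2.9 does not impute missing PK data. SAP 2.2 requires both a determinant baseline and at least one determinant post-baseline sample for the incidence set.

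**The concern.** Read together, the collection and classification rules treat the two assay results unequally. When no PK sample accompanies an irAE draw, a negative result is discarded and a positive result is kept. A percentage that mixes such samples with ordinary scheduled ones can only move up. The same clause reaches a case it does not fit. Missing PK is a reason to doubt a post-dose negative, because circulating drug can mask antibody. It is no reason to doubt a negative taken before any drug was given. What is at stake is the accuracy of a descriptive secondary endpoint (ADA prevalence at baseline and incidence on treatment) and the loss of some patients from the incidence set.

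**Working it through.** The documents give no figure for this rule, so there is nothing to reproduce. The check applies the definitions in SAP 2.10.1.1 to every combination of assay result and PK value.

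| ADA assay | PK missing | PK below tolerance | PK at or above tolerance |
|---|---|---|---|
| Positive | determinant, positive | determinant, positive | determinant, positive |
| Negative | inconclusive | determinant, negative | inconclusive |
| Not available | unevaluable | unevaluable | unevaluable |

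In the PK-missing column the only determinant outcome is positive. This follows from the definitions and needs no assumption about rates.

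**Which irAE samples fall in that column.** An irAE that is an SAE or ends treatment also triggers a PK draw. Table 6-9 requires permanent discontinuation for Grade 3 and 4 infusion reactions, so those are covered. It continues treatment after a Grade 1 reaction and after a first Grade 2 reaction, so unless serious these have no PK trigger. Where both draws are made, the SAP does not say how close in time the PK value must be to count as concurrent.

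**Effect if overall prevalence is counted by sample.** Let p be the positive share among scheduled determinant samples, taken to be also the true positive rate in irAE samples. Let r be the ratio of irAE samples without PK to scheduled determinant samples. Only the positive irAE samples enter, so the reported share is (p + rp) / (1 + rp). Neither p nor r is in the documents; the values below are assumptions that show the direction and scale.

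| Assumed p | r = 0.02 | r = 0.05 | r = 0.10 | r = 0.20 |
|---|---|---|---|---|
| 5% | 5.09% | 5.24% | 5.47% | 5.94% |
| 10% | 10.18% | 10.45% | 10.89% | 11.76% |
| 20% | 20.32% | 20.79% | 21.57% | 23.08% |

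For example, with p = 0.05 and r = 0.10: (0.05 + 0.005) / (1 + 0.005) = 0.0547.

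**Effect if counted by subject.** A patient with any other determinant sample is in the denominator whatever happens to the irAE sample. If the irAE sample is a confirmed positive, that patient is correctly called positive. An imbalance remains only for a patient with no other determinant sample: a positive irAE result admits that patient to the prevalence set in SAP 2.2, and a negative one does not.

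**Baseline.** Table 7-7 schedules paired PK and IG samples before the Cycle 1 infusion. SAP 2.9 sets results below the quantification limit to zero, so a baseline with a reported PK value of zero is not missing. Values flagged for exclusion are still used for ADA status (SAP 2.10.1.1). The problem therefore arises only when the baseline PK result is absent. A negative baseline is then inconclusive, the patient leaves the incidence set, and a later positive cannot be called treatment-induced, because that label needs an ADA-negative baseline. Exclusion criterion 3e bars prior PD-1- or PD-L1-directed therapy, so interference from earlier drug of this class is not a plausible reason for caution.

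**The case against.** The asymmetry is deliberate. The drug tolerance level is the highest concentration that does not interfere with detection, so a negative at an unknown drug level is properly doubtful and a positive is not. That defence stands for post-dose samples. It does not reach a sample taken before the first dose.

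A reader might infer more than the documents support, in three ways.

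- **That the plan will report ADA at irAEs as 100% positive.** SAP 2.10.1.1 plans summaries overall and by time point. It specifies no irAE time point and no table of ADA by irAE. The 100% describes the classification rule for samples without PK, not a planned output.
- **That overall prevalence is materially inflated.** This needs a by-sample count, which the SAP does not settle; the one denominator it defines is in subjects. The number of irAE draws without PK is unknown.
- **That these draws were meant to link ADA to hypersensitivity and now cannot show its absence.** No such purpose is stated; the objective is prevalence and incidence. Serious or treatment-ending events trigger PK, and paired pre-dose samples are scheduled at Day 1 of Cycles 1 to 13, so an infusion reaction on such a day should have a paired sample taken earlier that day. Footnote d to Table 7-7 also allows unscheduled PK at the investigator's discretion.

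If the note under Table 7-7 governs, every IG draw has a PK partner and the irAE part of the point falls away. The specific table entry, Table 7-1 and the Section 7.2.7 text all point the other way, so the conflict has to be resolved in the protocol.

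**Conclusion.** The point holds, at minor severity. It is certain from the definitions that an irAE sample without PK can be determinant only if positive, and that a negative pre-first-dose sample with a lost PK result is wrongly made inconclusive. The size is not known. The by-sample shift is upward and depends on counts the documents do not give; the by-subject effect is negligible for patients with other determinant samples. The number of patients lost through a missing baseline PK result is unknown and probably small. The drug tolerance level is not given either, so the share of negatives that paired PK would rescue cannot be stated. No test or success criterion depends on immunogenicity.

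**What to change.** 1. **Baseline (SAP 2.10.1.1).** State that the PDR001 concentration before the first dose is taken as zero, hence below the drug tolerance level, when the PK result is missing. A negative baseline then stays determinant.
2. **Collection (Protocol Tables 7-7 and 7-1).** Reconcile the IG-only entry with the note so that each irAE IG draw has a paired PK sample. For samples already banked, assay PDR001 in residual serum where volume allows.
3. **Summaries (SAP 2.10.1.1).** Leave irAE samples without PK out of both numerator and denominator of by-sample percentages, and report the number of inconclusive samples. Keep a confirmed positive in the patient's subject-level ADA status and in the listings. Dropping it there would lose a true positive and bias the subject-level figure downward.

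The cost is two SAP sentences, a table edit and a few assay runs; Section 7.2.7 allots 2 mL of blood to PK. A prospective change to collection needs a protocol amendment with ethics committee approval. It would affect few samples, because enrollment is complete and no further PK or IG samples are taken after 10-Aug-2018 unless the investigator requests them. The two SAP changes need no new blood and carry most of the benefit.
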